# 11.2 Statistical Analysis of Secondary Objective 1.2.1 Neurological, Endocrine and Cognitive

Objective: To explore potential associations of clinical and treatment factors with the incidence and severity of neurological, endocrine and cognitive deficits in children and young adults with ependymoma treated with a second course of irradiation.

To assess the side effects of radiation therapy in neurology, ophthalmology, audiology, endocrinology, and cognitive state, the data will be collected in a longitudinal setting. The time schedule for data collection is presented in Table 6.0.1 (Evaluations at baseline and follow-up). Since patients treated by focal or craniospinal radiation will be not at random, to compare the treatment effect, we need to adjust other clinical factors to limit the confound effects in the regression models as discuss below. In addition to the analysis plan below, once we have 15 patients in each stratum (a total of at least 45 patients) followed for 1 year, descriptive statistical analyses and regression analyses as discussed below will be conducted. The results of these interim analyses will be submitted for presentation at an appropriate national scientific meeting, as well as to the CT-SRC. There are not expectations that the findings of these interim analyses would raise concerns for the current trial.

**Neurology:** The neurologic signs and symptoms such as seizures, headache, motor sensation, ataxia, cranial nerve deficits and others will be collected. Neurological data will be obtained from the neurological protocol exam form. Grade 3-5 toxicity data as determined by the NCI CTCAE v 4.0 will be reported. The distribution of ordinal outcomes and percentages will be estimated. Mixedeffects Proportional Odds Regression [300] will be performed to estimate their changes over time, and compare severity in the two treatment arms adjusted by confound factors.

**Ophthalmology:** Vision status of a patient will be dichotomized into None and Impaired, according to clinical meanings, as described in Section 6.3. We will

St. Jude Children's Research Hospital IRB NUMBER: Pro00004349

IRB APPROVAL DATE: 02/01/2023

also use the information recorded in the clinical neurology form (see appendix) and NCI CTCAE v4.0 when relevant. The percentages for both statuses will be estimated. Generalized Estimating Equations (GEE) with logistic link will be employed to estimate the change of vision over time, and compare severity of vision in the two treatment groups adjusted by confound factors.

**Audiology:** To assess hearing loss in patients, hearing will be dichotomized as normal if all thresholds are within 0-20 DB HL and otherwise abnormal. GEE with logistic link will be modeled to explore the trend over time and investigate impacts of specific clinical and treatment factors on hearing loss. In the presence of missing data, Weighted GEE will be employed to address missingness. In addition, the cumulative incidence of hearing loss will be estimated with death as a competing risk. Chang Ototoxicity Grading Scale (COGS) will also be used to evaluate the hearing loss. The ordinal COGS will be analyzed similarly as Neurology grade.

**Endocrine:** Endocrine data as a continuous variable will be collected. Descriptive statistical analysis will be performed. Diabetes Insipidus (DI) is a hormone deficiency that results only from direct damage to the hypothalamus and pituitary axis (mainly pituitary stalk) by tumor or surgery. This longitudinal binary variable (coded as "yes" or "no") will be compared between the surgery and radiation groups using GEE adjusted by other confounding factors. Hormone Deficiency, such as Growth Hormone Deficiency (GHD), will be compared between the surgery and radiation groups. Growth hormone will be dichotomized with GHD=1 for <7ng/ml and GHD=0, otherwise. We define GHD=1 as event. Since the treatment of other hormone deficiency could be a compete risk for this event, cumulative incidence regression analysis using Fine and Gary method will be employed [301]. Specific clinical and treatment group factors will be included as covariates to investigate the treatment group difference. Other Hormone Deficiency, including Thyroid Hormone Deficiency (central hypothyroidism), Adrenal Insufficiency, Gonadotropin Deficiency or Precocious Puberty, Diabetes Insipidus, Hypothalamic Obesity (not a specific endocrine deficiency but an endocrine problem nonetheless), will be analyzed similarly. Some of these measures are graded in the NCI CTCAE v4.0.

**Neurocognitive:** Neurocognitive measures are continuous. GEE will be employed to estimate treatment group difference with specific clinical factors and time also included as covariates. For some neurocognitive measures, children and young adults (adolescents) will have different forms. When we pool data together to perform the analysis, we will take these differences into account in the GEE model to control for variations. Neurocognitive measures will also be dichotomized into normal and abnormal groups based on cut-off values (average range vs. outside of the average range for a given test instrument) at specific time points after therapy. GEE with logistic link will be used to investigate the treatment group effect. Frequency and percentage of dichotomized cognitive measures will be calculated.

St. Jude Children's Research Hospital IRB NUMBER: Pro00004349

IRB APPROVAL DATE: 02/01/2023

IRB Approval date:

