#### 3.1 Inclusion Criteria

- Progressive intracranial ependymoma after prior focal irradiation
- Patients aged 1-21 years at the time of enrollment
- Adequate performance status (ECOG < 3) and research participant does not require mechanical ventilation
- Interval from start of initial radiation therapy to enrollment > 9 months

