#### 4.3 **Stratification for Treatment**

Stratification for treatment of ependymoma will be determined when radiation therapy planning is initiated. There is no limit to the number of participants in each stratum.

Stratum 1 (initial pattern of failure is local); disease confined to primary site; age >12 months at time of enrollment to < 21 years. Treatment: focal irradiation.

Stratum 2 (initial pattern of failure is metastatic); neuraxis metastatic disease without equivocal evidence of local failure; age > 36 months at time of enrollment to < 21 years. Treatment: craniospinal irradiation.

Stratum 3 (initial pattern of failure is both local and metastatic): neuraxis metastatic disease with unequivocal evidence of local failure; age > 36 months at time of enrollment to < 21 years. Treatment: craniospinal irradiation.

Stratum 4 (initial pattern of failure is local): disease confined to primary site; age >36 months at time of enrollment to < 21 years; tumor shows presence of 1q gain. Treatment: craniospinal irradiation (optional).

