# 6.4 Audiology

Schedule: Patients will be referred for audiological testing prior to radiation therapy and annually dated from the start of RT. More frequent evaluations may be considered by the treating physician or audiologist based on results of prior evaluations and the potential risk for hearing loss.

Tests and Outcome Measurements: At each evaluation tympanometry will be performed to assess integrity of the conductive mechanism, distortion product otoacoustic emissions will be assessed to determine cochlear outer hair cell function, a pure tone audiogram will be obtained to assess peripheral hearing sensitivity, and speech-in-noise testing will be administered to assess performance in background noise and to screen for auditory processing disorder in children. Each audiogram will include air conduction thresholds at 250, 500, 1000, 2000, 3000, 4000, 6000, and 8000 Hertz measured in dB HL. Ultra-high frequency thresholds will be obtained at 9000, 10000, 11200, 12500, 14000, and 16000 Hertz in patients older than 5 years. Bone conduction thresholds will be obtained as needed to rule out a conductive component to the hearing impairment. Hearing will be categorized as normal if all thresholds are within the 0-20 dB HL range. If a deficit is present, hearing impairment will be categorized by the numerical dB HL values. Speech-in-noise testing will be administered to patients older than 5 years. The QuickSIN speech-in-noise test [219] will be administered to patients older than 14 years and the BKB-SIN speech-in-noise test [220] will be used for patients 5-14 years and for adults whom the QuickSIN test is too difficult.

St. Jude Children's Research Hospital

IRB NUMBER: Pro00004349
IRB APPROVAL DATE: 02/01/2023

Rev. 3.2 dated: 1/19/2023

An auditory brainstem response (ABR) evaluation may be substituted for patients who are unable to respond to conventional audiometric testing techniques.

Every audiogram or ABR evaluation will be assigned a grade based on the Chang and SIOP Ototoxicity Grading Scales.

Ototoxicity Grading Scales\*

	Chang	SIOP					
Grade 0	$\leq$ 20 dB at 1, 2, and 4 kHz	Grade 0	≤20 dB HL at all frequencies				
Grade 1a	$\geq$ 40 dB at any freq 6 to 12 kHz		>20 dB HL (i.e., 25 dB HL or				
Grade 1b	> 20 and < 40 dB at 4kHz	Grade 1	greater) SNHL above 4000 Hz (i.e., 6 or 8 kHz)				
Grade 2a	≥ 40 dB at 4 kHz and above		>20 dB HL SNHL at 4000 Hz and				
Grade 2b	> 20 and < 40 dB at any freq below 4kHz	Grade 2	above				

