Grade 3	≥ 40 dB at 2 or 3 kHz & above	Grade 3	>20 dB HL SNHL at 2000 Hz or 3000 Hz and above				
Grade 4	≥ 40 dB at 1 kHz and above	Grade 4	>40 dB HL (i.e., 45 dB HL or more) SNHL at 2000 Hz and above				

\*Sensorineural Hearing Threshold (dB HL) bone conduction or air conduction with normal tympanogram

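### The binary hearing rule gets stricter when a child passes age 5, so apparent hearing loss can arise with no change in hearing

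*Combined protocol and SAP*

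**What the plan says.** Section 11.2 (Audiology) sets the analysis rule: "hearing will be dichotomized as normal if all thresholds are within 0-20 DB HL and otherwise abnormal". Section 6.4 has the same rule: "Hearing will be categorized as normal if all thresholds are within the 0-20 dB HL range". Neither sentence names a frequency set.

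The set tested depends on age. Section 6.4 gives a core set, "Each audiogram will include air conduction thresholds at 250, 500, 1000, 2000, 3000, 4000, 6000, and 8000 Hertz measured in dB HL", and then an extension: "Ultra-high frequency thresholds will be obtained at 9000, 10000, 11200, 12500, 14000, and 16000 Hertz in patients older than 5 years". In 6.4 the rule for normal hearing comes after both lists.

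On timing, "Patients will be referred for audiological testing prior to radiation therapy and annually dated from the start of RT"; the evaluation tables run audiometry yearly to month 60. On age, section 3.1 admits "Patients aged 1-21 years at the time of enrollment". In section 4.3 the focal stratum opens above 12 months, while the strata offering craniospinal treatment carry the condition "age > 36 months at time of enrollment to < 21 years. Treatment: craniospinal irradiation" (optional in the 1q-gain stratum).

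Section 11.2 uses the binary outcome in a logistic GEE for the time trend and for clinical and treatment factors, and in a cumulative incidence estimate with death competing.

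**The concern.** An outcome that requires every threshold to be normal becomes harder to satisfy each time a threshold is added. Here the addition is triggered by a birthday that falls inside follow-up for any child enrolled at 5 or younger and followed long enough. The switch coincides with time since irradiation, which is the axis of the GEE trend and of the cumulative incidence. A reader would take the result as ototoxicity.

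The focal and craniospinal groups have different age floors and may hold different shares of young children, so the artefact need not cancel between them. Section 11.2 also plans regression analyses for presentation at a scientific meeting once 15 patients per stratum have one year of follow-up. That is when the groups would differ most in the share still on the short frequency set.

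**Working it through.** The plan gives no hearing-loss rate, sample size or power for this outcome, so there is no figure to reproduce. The direction follows from the rule. The sizes below are illustrations.

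**Direction.** Let S mean abnormal at 250-8000 Hz and U mean abnormal at 9-16 kHz. Up to age 5 the outcome is S; after age 5 it is S or U. With hearing unchanged, the increase is P(U and not S), which is zero or positive.

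**Size of the step.** From 6.4, there are 8 frequencies up to age 5 and 8 + 6 = 14 after; for two ears, 16 and 28 thresholds. Assume each threshold is independently abnormal with probability p. Then P(abnormal) = 1 - (1 - p)^k.

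| p (assumed) | k = 16 | k = 28 |
|---|---|---|
| 1% | 14.9% | 24.5% |
| 2% | 27.6% | 43.2% |
| 5% | 56.0% | 76.2% |

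Real thresholds are correlated, which shrinks the step. With perfect correlation it is zero.

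**Effect on the group comparison.** Hold every child's hearing constant and follow all to month 60. Let s be the share abnormal at 250-8000 Hz (assumed 20%), u the chance of an isolated 9-16 kHz abnormality in a child normal at 250-8000 Hz (assumed 30%), and F the share aged 5 or younger at entry.

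- Baseline prevalence = s + (1 - s) × u × (1 - F).
- Month-60 prevalence, when all are past 5, = 0.20 + 0.80 × 0.30 = 44% in both groups.
- False 5-year incidence among those normal at baseline = uF / [1 - u(1 - F)].

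The documents give age floors but no age distribution, so F is assumed in two ways. Uniform ages to 21 give F = 4/20 = 20% (focal, from 1 year) and 2/18 = 11.1% (craniospinal, from 3 years). A young-skewed distribution cut at the same floors gives about 46% and 34%.

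| | Focal | Craniospinal |
|---|---|---|
| Baseline, uniform | 0.20 + 0.24 × 0.80 = 39.2% | 0.20 + 0.24 × 0.889 = 41.3% |
| Baseline, young-skewed | 0.20 + 0.24 × 0.54 = 33.0% | 0.20 + 0.24 × 0.66 = 35.8% |
| False incidence, uniform | 0.060/0.760 = 7.9% | 0.0333/0.7333 = 4.5% |
| False incidence, young-skewed | 0.138/0.838 = 16.5% | 0.102/0.802 = 12.7% |

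The rise from baseline to month 60 is 44.0 - 39.2 = 4.8 points focal against 44.0 - 41.3 = 2.7 craniospinal (uniform), or 11.0 against 8.2 (young-skewed).

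For u from 10% to 50% across both age assumptions, the craniospinal excess at baseline is about 1 to 5 points and is gone by month 60. False incidence is higher in the focal group throughout: 2.2% against 1.2% at the low end (uniform, u = 10%) and about 31% against 25% at the high end (young-skewed, u = 50%).

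**With a fixed set.** If the outcome is S at every age, prevalence stays at 20% in both groups at every visit and there are no false events.

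**The case against.** The strongest reply is that the plan already limits the damage. Section 11.2 adjusts for clinical factors, offers weighted GEE for missing data, and also analyzes the ordinal Chang grade. Each helps only in part. The adjustment names neither age nor frequency set, and adjusting for age at entry would not remove a definition that switches within a child. Frequencies not tested by design are not described as missing. Most Chang grades rest on 4 kHz or below, but grade 1a uses 6 to 12 kHz and so is partly exposed. By contrast, the neurocognitive paragraph of 11.2 does promise to account for age-dependent forms.

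Several stronger readings are tempting and are not supported:

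- **That the craniospinal group will look worse.** This holds at most for prevalence at early visits. For incidence and slope the direction reverses. The documents give age floors, not age distributions by group.
- **That children under 5 are typical here.** Section 2.1 gives age at initial treatment, and the historical data give time from first irradiation to failure. Section 4.1 sets no limit on the interval from failure to enrollment and allows several progressions. Young children are plausible, but their share is undocumented.
- **That middle-ear fluid will count as hearing loss.** Section 6.4 requires tympanometry at each evaluation and bone conduction as needed to rule out a conductive component. What is missing is a statement that the binary rule uses the convention attached to the grading scales, "Sensorineural Hearing Threshold (dB HL) bone conduction or air conduction with normal tympanogram".
- **That thresholds better than 0 dB HL count as abnormal.** This is an over-literal reading; the grading table in the same section sets grade 0 at 20 dB or less.

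It is also fair that ABR may replace audiometry in children who cannot be tested conventionally, so not every early visit yields the eight core thresholds. The fix has to cover those visits.

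**Conclusion.** The point stands as a defect in a stated rule. The definition of normal hearing tightens at age 5 during follow-up, and with stable hearing this can only push the GEE trend and the cumulative incidence upward. It can also distort the focal versus craniospinal comparison: possibly higher craniospinal prevalence early on, and possibly more false incident loss and a steeper slope in the focal group, if the focal group is in fact younger.

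The size cannot be found from the documents. It depends on how often 9-16 kHz is abnormal alone and on how many children enter at 5 or younger. The 15% to 25% step rests on 1% independent thresholds in two ears; the group figures rest on assumed ages and rates. Severity is low to moderate: the objective is exploratory, and no sample size or stopping rule depends on this outcome.

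**What to change.** In sections 6.4 and 11.2:

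1. Define the binary outcome on one set at every age: normal if all thresholds at 250-8000 Hz are 20 dB HL or better, using the sensorineural convention already stated for the grading scales.
2. Analyze 9-16 kHz as a separate outcome in patients older than 5 years at baseline.
3. State how ABR visits, and hearing already abnormal at baseline, enter the GEE and the cumulative incidence.

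The cost is a few sentences and no new testing, since the thresholds and tympanometry are already planned. The drawback is that early loss confined to 9-16 kHz would appear only in the separate outcome, and only for children older than 5 at baseline.

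### The Endocrine analysis in Section 11.2 compares a surgery group with a radiation group, but the trial defines no such groups

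*Combined protocol and SAP*

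**What the plan says.** Three statements in the Endocrine paragraph of Section 11.2 matter here.

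- Diabetes insipidus, a longitudinal yes/no variable, "will be compared between the surgery and radiation groups using GEE adjusted by other confounding factors".
- The next sentence gives a second endpoint the same contrast: "Hormone Deficiency, such as Growth Hormone Deficiency (GHD), will be compared between the surgery and radiation groups". This is to be done by cumulative incidence regression with the Fine-Gray method.
- A list of other deficiencies is to be handled in the same way. It covers thyroid and adrenal deficiency and also "Gonadotropin Deficiency or Precocious Puberty, Diabetes Insipidus, Hypothalamic Obesity". Diabetes insipidus thus appears a second time, now under the cumulative incidence approach.

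The same paragraph says that diabetes insipidus "results only from direct damage to the hypothalamus and pituitary axis (mainly pituitary stalk) by tumor or surgery".

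The rest of Section 11.2 uses a different grouping. Its opening, which covers endocrinology by name, motivates covariate adjustment with "Since patients treated by focal or craniospinal radiation will be not at random". The Neurology paragraph then plans to "compare severity in the two treatment arms adjusted by confound factors". Section 11.3 spells out the arms as focal against craniospinal irradiation.

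**The concern.** A between-group comparison needs two groups with patients in them. This is a single-cohort, non-randomised study of surgery followed by a second course of irradiation, so the two modalities are given together and are not alternatives. If every analysed patient is irradiated, a surgery group set against a radiation group has no members, and neither the GEE nor the Fine-Gray group coefficient is defined.

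Endocrine deficit is a named part of secondary objective 1.2.1. Section 11.2 also schedules these regressions at an interim point, for a national meeting and the CT-SRC, so the wording applies before the final analysis. An analyst following the paragraph would have to choose the contrast with data in hand and, for diabetes insipidus, the main method as well.

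**Working it through.** The plan gives no sample size, power or other figure for this comparison, so there is nothing to reproduce. The check sets the sections side by side.

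**1. Endpoints carrying the contrast.** Named directly: diabetes insipidus and growth hormone deficiency. Inherited: thyroid deficiency, adrenal insufficiency, gonadotropin deficiency or precocious puberty, and hypothalamic obesity. Distinct endpoints: 2 + 4 = 6.

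**2. Who is irradiated.**
- Section 4.3: stratum 1 is focal, strata 2 and 3 are craniospinal, and stratum 4 has craniospinal as an option. Section 5.7.1 makes that an option in place of focal treatment. Irradiated strata: 4 of 4. Surgery-only strata: 4 − 4 = 0.
- Section 5.3: enrolled patients receive radiation therapy. Surgery usually comes first.
- Objective 1.2.1: the population is patients treated with a second course of irradiation.

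**3. Could another grouping be meant?**
- Section 4.1 recommends surgery without requiring it. A split on that basis gives surgery plus radiation against radiation alone. The plan does not define that split, and it is not what the Endocrine paragraph says.
- Section 4.2 wants the impact of surgery on functional outcomes, including endocrine outcomes. It describes assessment at enrollment and again after surgery, which is a within-patient comparison.
- Definition 1.4.3 mentions radical surgery or limited surgery with radiation. No stratum or analysis group corresponds to it.

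**4. The contrast used elsewhere.** The opening of Section 11.2 and Section 11.3 name focal versus craniospinal irradiation. The two arms in Neurology and the two groups in Ophthalmology fit that. The growth hormone text itself goes on to speak of a treatment group difference with clinical and treatment covariates.

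**5. Would the replacement contrast have patients in it?** Assume that the 90 planned patients follow the historical mix in Table 11.0, with 22 focal and 7 + 16 + 5 = 28 craniospinal of 50.
- Historical mix: 90 × 22/50 = 39.6 focal and 90 × 28/50 = 50.4 craniospinal.
- All local failures (22 + 7 = 29) treated focally: 90 × 29/50 = 52.2 focal and 90 × 21/50 = 37.8 craniospinal.

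Both groups are well populated in either case. These figures show that the fix is feasible. They do not measure the defect. The absence of unirradiated patients from the historical cohort adds no evidence, because that cohort was selected as re-irradiated.

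**6. Would surgical covariates vary?** In Section 11.0, 34 of 50 had gross total resection and 9 + 7 = 16 did not. On the same assumption, 90 × 34/50 = 61.2 and 90 × 16/50 = 28.8.

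**The case against.** The strongest reply is that the intended model is recoverable. The opening of Section 11.2 sets focal against craniospinal, with adjustment, for the whole section including endocrinology, and the growth hormone text returns to that language. Definition 1.4.2 already counts type and extent of surgery as treatment factors. On this view the defect is a slip in one paragraph of an exploratory analysis. Much of that stands. It limits the consequence but does not make the stated contrast estimable, and it does not settle diabetes insipidus.

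A second reply is that a question about surgery does exist. Section 4.2 calls the impact of surgery on functional outcomes an important exploratory objective. That also stands. It is why the surgery wording should not be deleted without asking whether a surgery effect was meant.

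A reader might infer that no enrolled patient could have surgery without irradiation. The documents do not support that. Section 4.1 prefers enrollment before surgery, Section 4.4 sets no time limit to irradiation, and Sections 4.1 and 8.1 give several reasons for leaving the study, any of which could come first. Such patients fall outside objective 1.2.1 and are nowhere defined as a comparison group.

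**Conclusion.** The concern holds. The Endocrine paragraph names a contrast that has no counterpart in the trial's strata, treatment sections or objective 1.2.1, and no alternative reading of the protocol supplies one. It affects six named endpoints. No sample size, power or decision rule depends on it. The objective is exploratory, and the primary PFS and OS analysis is untouched. It is a modest correction that should be made.

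Two stronger readings are tempting and go too far. One is that the endocrine objective cannot be met. The data and a workable contrast are both already in the plan, so only the wording fails. The other is that diabetes insipidus was certainly meant to be analysed by surgical factors. The plan's account of its cause makes a surgery effect plausible, but nothing states that intent.

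The conclusion itself rests on the text alone. Only the projected group sizes assume that the prospective mix resembles the historical one.

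**What to change.** In the Endocrine paragraph of Section 11.2:

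1. Replace the surgery-versus-radiation grouping with focal versus craniospinal irradiation, adjusted for clinical and treatment factors as Section 11.2 already provides.
2. If a surgery effect is intended for diabetes insipidus or any other deficiency, define it explicitly. One option is to enter surgical factors that the protocol already collects, such as extent of resection and previous procedures, as covariates.
3. State whether GEE or the Fine-Gray regression is the main analysis of diabetes insipidus. Both may be kept if one is named as main.

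The cost is a wording change to the SAP. Irradiation volume and surgical details are already recorded under Definition 1.4.2 and Section 4.2, so no new data, visits or patients are needed.

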## 2.2 Neurological, Endocrine and Cognitive Studies

Neurological, endocrine and cognitive effects of irradiation are the most common focus of concern for caregivers. Neurological effects most often include cranial nerve, motor and cerebellar dysfunction. The effects of surgery and irradiation on neurological function have been previously described for children with ependymoma initially treated with aggressive surgery and irradiation [18]. There is little doubt that patients who experience tumor recurrence and undergo additional surgery and radiation therapy will experience or be susceptible to treatment effects. These have not been formally documented. Such documentation will be the goal for this study both to describe the morbidity of the condition as well as to identify clinical covariates that impact other measures of CNS effects. Neurological deficits include transient and permanent damage to hearing and

IRB Approval date:

Rev. 3.2 dated: 1/19/2023 Protocol document date: 1/19/2023 St. Jude Children's Research Hospital

IRB NUMBER: Pro00004349

vision and loss of neurological function associated with surgery, radiation therapy and in the extreme – necrosis of brain or spinal cord.

The endocrine effects of retreatment may compound the existing risk for any endocrinopathy which ranges up to 25% among patients successfully or unsuccessfully treated with initial surgery and irradiation [7]. Because most recurrences after initial treatment occur about 18-26 months after treatment, patients enrolled on this study may have ongoing endocrine deficiencies that need to be addressed and document to assess the toxicity of the proposed treatment regimen. Children will undergo endocrine evaluation and provocative assessment of growth hormone and adrenal axis hormones.

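### The endocrine incidence analysis uses treatment of other hormone deficiencies as the competing risk and does not name death, and neither it nor the hearing-loss incidence excludes deficits present before re-irradiation

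*Combined protocol and SAP*

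**What the plan says.** Section 11.2, Endocrine, defines the event by a cut-off: "Growth hormone will be dichotomized with GHD=1 for <7ng/ml and GHD=0, otherwise. We define GHD=1 as event". The only competing risk it names is in "Since the treatment of other hormone deficiency could be a compete risk for this event", and it continues that "cumulative incidence regression analysis using Fine and Gary method will be employed". The remaining deficiencies follow the same method; the list ends "Hypothalamic Obesity (not a specific endocrine deficiency but an endocrine problem nonetheless), will be analyzed similarly". Death is not named for any endocrine endpoint.

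Section 11.2, Audiology, defines the outcome as status too: "hearing will be dichotomized as normal if all thresholds are within 0-20 DB HL and otherwise abnormal". Here death is named: "the cumulative incidence of hearing loss will be estimated with death as a competing risk".

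Neither paragraph gives an at-risk set, a baseline exclusion or a change-from-baseline rule for the incidence analysis. Section 2.2 says that "patients enrolled on this study may have ongoing endocrine deficiencies" and puts the existing risk of any endocrinopathy after initial treatment at up to 25%. Baseline audiology (Section 6.4) and baseline endocrine testing (Section 6.5) are already scheduled.

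**The concern.** A competing event is one after which the event of interest can no longer happen. A child treated for another deficiency can still become growth hormone deficient. If that treatment is coded as a competing event, a GHD that follows it is not counted, and the curve estimates GHD occurring before treatment of any other deficiency. A child who dies can no longer develop GHD, yet the handling of death is left open. The neighbouring Audiology paragraph does specify it.

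The second gap is the risk set. Every participant has had focal irradiation. The secondary hypothesis in Section 1.2 concerns side effects after the second course and their relation to treatment factors. An absolute cut-off without a baseline restriction can mix deficits from the first course with deficits that arise after re-irradiation.

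At stake are the incidence figures and group contrasts reported under Objective 1.2.1. The primary PFS and OS analysis is not affected.

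**Working it through.** The plan states no GHD or hearing-loss incidence, so there is no figure to reproduce. The sizes below are illustrations.

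**Inputs from the documents.** Historical OS in Table 11.1 is 0.979, 0.778, 0.704, 0.607 and 0.569 at years 1 to 5. As a check, a life table on the printed counts with half-interval censoring gives 0.979, 0.777, 0.698, 0.605 and 0.569, which agrees closely. Growth hormone provocative tests are at baseline, 12 and 24 months (Section 6.5, Tables 6.0.1 and 6.0.2). Appendix III lists this test at baseline only and should be reconciled; I use Section 6.5. Endocrine clinic visits run to month 60 (Table 6.0.2).

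**Assumptions.** The deficiency hazard h is constant and independent of death. The documents give no value, so I use a range.

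**Step 1: death censored or competing, constant hazards.** Death hazard d = -ln(0.569)/5 = 0.113 per year. With death censored, apparent incidence is 1 - exp(-hT). With death competing, it is h/(h+d) × [1 - exp(-(h+d)T)].

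| h per year | T = 2: censored / competing | Gap, points | T = 5: censored / competing | Gap, points |
|---|---|---|---|---|
| 0.05 | 9.5% / 8.5% | about 1 | 22.1% / 17.1% | about 5 |
| 0.10 | 18.1% / 16.3% | about 2 | 39.3% / 30.8% | about 9 |
| 0.20 | 33.0% / 29.7% | about 3 | 63.2% / 50.5% | about 13 |

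**Step 2: the same comparison on the printed OS curve.** Here survival S(t) is piecewise exponential through the Table 11.1 values, h is set so that 1 - exp(-hT) equals an assumed net risk, and incidence with death competing is the integral of h·exp(-ht)·S(t) from 0 to T. For net risks of 20%, 40% and 60%:
- At 2 years: 18.7%, 37.7% and 56.9%, gaps of 1.3, 2.3 and 3.1 points.
- At 5 years: 15.6%, 31.6% and 48.5%, gaps of 4.4, 8.4 and 11.5 points.

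Together, steps 1 and 2 give about 1 to 3 points at 24 months and 4 to 13 points at 5 years.

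**Step 3: progression.** Section 8.1 lists progression as an off-study criterion. If testing stops there, replacing S(t) by the Table 11.1 PFS curve gives 2-year values of 15.4%, 31.3% and 47.6% for the same net risks. How progression is handled therefore matters more at 24 months than how death is handled.

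**Step 4: prevalent cases.** With baseline prevalence p and true new incidence n among patients free at baseline, the apparent incidence is p + (1 - p)n. For n = 20%:
- p = 5%: 0.05 + 0.95 × 0.20 = 24%.
- p = 10%: 0.10 + 0.90 × 0.20 = 28%.
- p = 25%: 0.25 + 0.75 × 0.20 = 40%.

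The 25% is the Section 2.2 upper figure for any endocrinopathy. It is not an estimate for GHD, and the documents give none for hearing.

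**Step 5: direction.** Censoring death and counting prevalent cases both raise the estimate. Coding other hormone treatment as a competing event lowers it, because later GHD is dropped. The documents give no rate of such treatment, so that effect cannot be sized.

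**Step 6: group contrast.** The historical 5-year OS in Section 11.0 is 0.533 for local failure with focal treatment (n = 22), 0.802 for distant failure with craniospinal irradiation (n = 16) and 0.250 for combined failure with craniospinal irradiation (n = 5). The numbers are small, but if death rates differ in this way, the meaning of the Fine-Gray treatment coefficient depends on how death is coded.

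**The case against.** The best defence of the named competing risk is that hormone treatment affects whether GHD can be seen. Section 6.5 allows tests to be omitted in patients on replacement and calls overall endocrine status critical to interpreting the growth hormone data. That explains the wording, but an untested child may still be deficient. This is a missing observation, possibly an informative one, and it does not preclude the event.

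Naming one competing risk does not say that death is censored. That is true, so the sizes in steps 1 and 2 are conditional. The handling of death still has to be stated, as it is for hearing.

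A reader might infer that the plan counts existing deficits as events at time zero, that up to a quarter of patients would be such events, and that the resulting incidence is wrong. The documents do not support this. Section 11.2 is silent on prevalent cases, incidence is ordinarily computed among patients free of the event, and some patients on replacement may go untested and be missing. Nor does the 5-year death effect apply to GHD by provocative testing, which ends at 24 months.

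Section 2.1 ranks toxicity of the combined regimen above attribution to earlier treatment. That supports reporting total burden as well, and separate baseline prevalence serves both aims. Hearing loss already has death as a competing risk and longitudinal models, including one for the ordinal Chang grade. Only its cumulative incidence lacks an at-risk definition.

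**Conclusion.** The concern holds in this form. The competing event for GHD, and by extension for the other hormone deficiencies, is wrong as written, and death should take its place. The missing at-risk definition is a gap in specification that leaves room for overstatement.

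If prevalent cases are counted, the overstatement is 4 to 20 points on a true 20%, for prevalence of 5% to 25%. If death is censored, it is about 1 to 3 points at 24 months and 4 to 13 points at 5 years. These figures rest on historical survival, assumed constant deficiency hazards and independence from death. The net bias of the analysis as written has no fixed sign, because the competing event it names works in the opposite direction.

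The objective is secondary and exploratory, with no decision rule attached. The correction should be made, but it does not touch the primary objective.

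**What to change.** In Section 11.2:

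1. Name death as the competing event for GHD and for every endocrine endpoint analysed in the same way.
2. State how progression is handled when it ends testing: as a competing event or as censoring, with the reason.
3. Stop coding treatment of other hormone deficiencies as a competing event. Treat tests skipped because of replacement as missing observations, report their number, and adjust for replacement status at baseline only. Replacement started during follow-up is an internal time-dependent covariate, which Fine-Gray regression handles poorly.
4. Restrict the GHD, other endocrine and hearing-loss incidence analyses to patients free of the deficit at the pre-irradiation test, or define the event as worsening from baseline (for hearing, a higher Chang grade). Give a rule for patients with no baseline test.
5. Report baseline prevalence separately.

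The cost is SAP wording, since the baseline tests are already scheduled. The price is fewer patients at risk and wider intervals. Section 11.2 plans interim regression analyses for presentation at a scientific meeting, so the definitions should be fixed before results are reported.
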